5. GENERAL STATISTICAL METHODS

This section describes the general statistical methods for the study, such as sample size estimation, reporting of patient's disposition and protocol deviations and the statistical methods to be applied in demographics and baseline characteristics, efficacy and safety analyses.

Interim analyses are planned for this study. Details can be found in section 5.3.5.

Safety Committee Meetings as well as DMC are planned for this study. Details can be found in section 5.3.6.

Data handling and missing data handling as well as reporting conventions are described in sections 5.3.8, 5.3.9 and 5.3.11 respectively.

5.1 Sample Size

A study of IFN- α 2 in a population with inactive CHB reported a mean incremental decrease of 1.3 log-qHBsAg at 24 weeks in those patients completing IFN- α 2 treatment compared to non-treatment. Mean decrease would translate to approximately 50% of patients completing treatment achieving 1.3 log-qHBsAg response (reduction). To estimate treatment effect in the current study, the proportion of patients achieving a 1.0-log reduction in qHBsAg is estimated as one-half (25% of patients) who achieve this response. Assuming a response rate of 3% on placebo and 25% on HepTcell, 40 patients will be randomized per treatment group to detect a difference in the proportion of patients treated with HepTcell

achieving the primary endpoint compared to patient treated with placebo at a 0.05 level of significance (two-sided) with approximately 80% power.

5.2 Patient disposition

5.2.1 Patient disposition and withdrawals

This section describes patient disposition.

Screened patients include all patients who signed the informed consent form and are entered into the clinical database.

Re-screened patients include all patients who were declared screening failures at their first screening but were screened in a subsequent requalification.

Randomized patients will include all patients who were provided a treatment assignment that was recorded in the interactive response technology database, regardless of whether the treatment kit was used.

For patients' study status, the total number and percentage of patients in each of the following categories will be presented in the CSR using a flowchart diagram or summary table:

- Screened patients
- Re-screening patients among screened patients.
- Screen failure patients.
- Nonrandomized but treated patients (if applicable).
- Randomized patients.
- Randomized but not treated patients (if applicable).
- Patients in the mITT Population.
- Patients in the Safety Population.
- Patients in the PP Population.
- Patients who discontinued study treatment early, including primary reason for discontinuation.
- Patients who discontinued study early, including primary reason for discontinuation.

For all categories of patients (except for the screened and nonrandomized categories) the summaries will be provided by randomized treatment arms, and percentages will be calculated using the number of randomized patients as the denominator.

The number (%) of patients in each population will also be summarized by treatment. They will also be listed. The number of mis-stratified patients will be listed.

A listing of patients with population assignment including individual reasons of exclusion from the respective analysis populations will be provided. Data listing for early termination reasons will be also provided.

22-Apr-2024

5.2.2 Protocol Deviations

Protocol deviations, including violations of inclusion/exclusion criteria, will be collected, and assessed as "minor" or "major" by the study team and the final version will be provided to the biostatistics contract research organization (Pivotal) prior to the database locks (1)- When all patients complete the Day 169 assessments or terminate the trial; (When all patients complete the Day 505 assessments or terminate the trial). Where it is programmatically possible deviations will be verified programmatically from the database. Statistically significant deviations will be identified by the sponsor and project team prior to each database lock. These are defined as deviations which have the potential to have a significant impact on the statistical analysis and interpretation of the study data.

All protocol deviations will be collected separately from the database and listed. The final listing of protocol deviations will be reviewed before each database lock to assist in the Per Protocol population selection and definition of the final study populations as well as a preliminary assessment of the quality of the trial data. All deviations will be summarized by deviation type and listed in the CSR.

5.3 Summary of Statistical Methods

This study is designed as a phase 2 study, exploratory in nature, to evaluate the response to HepTcell in treatment-naïve patients with inactive CHB. Comparisons will be performed between HepTcell and Placebo at a two-sided type I error rate of 0.05 which will not be adjusted for multiple testing.

The study will be considered to have achieved proof-of-concept when the 2-sided p-value is <0.05. Accordingly, the primary and key secondary efficacy endpoints will present 2-sided 95% Confidence Intervals (95%Cls) when applicable.

Unless otherwise specified, efficacy analyses will be performed using the mITT population, where patients will be in the treatment arm to which they received. As described in more detail elsewhere, patients will be analysed according to the treatment of the most treatment received. Moreover, supportive efficacy analyses will be performed in the PP population. Safety related analyses will use the safety population, where patients will be analyzed according to the treatment that they receive.

All applicable baseline data will be summarized by treatment arm (HepTcell, placebo), unless specified otherwise. Safety and efficacy data will also be summarized by treatment arm and additionally by time-point of assessment and/or follow-up, when appropriate.

Continuous variables will be summarized using the number of observations (n), mean (95%CI, if appropriate), standard deviation (SD), Standard error (SE, if appropriate), median, first quartile (Q1), third quartile (Q3), minimum, and maximum along with the total number of patients contributing values.

Descriptive statistics for categorical/qualitative data will include frequency counts and percentages. The denominator for all percentages will be the total number of patients in the treatment arm and dose number (if applicable) within the population of interest, unless stated otherwise in the table footnote.

Change from baseline is calculated only for patients with non-missing values for both the baseline and the time-point of interest and will be missing otherwise.

Statistical comparisons will be performed between HepTcell and placebo at a 5% confidence level.

All relevant patient data will be included in listings. All patients entered into the database will be included in patient data listings. The listings will be generally sorted by treatment arm and then Patient ID, unless specified otherwise.

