6.1.2. Packaging, Storage, and Handling

All supplies are labelled as investigational products (IPs) in accordance with applicable legal and regulatory requirements. All IPs will be stored in a secure place under appropriate storage conditions.

FP-02.2 (0.36 mg per vial or each peptide) supplied in 2 mL single-use glass vials is stored at -20°C \pm 5°C.

28 mM L-histidine diluent (1.2 mL) supplied in 2 mL single-use glass vials is stored at 2-8°C.

IC31 (1000 nmol/mL KLK; 40 nmol/mL ODN1a) (1.6 mL) supplied in 2 mL single-use glass vials is stored at 2-8°C.

All components will be brought to room temperature before dose preparation.

In the US, Canada, Spain, Thailand, and Italy reconstitution of IP will be performed by unblinded staff at the site. In the UK and Germany, reconstitution of IP will be done at a centralized location. Please refer to the ALT-301-202 Pharmacy Manual for more information.

Use of gloves is recommended when removing material from vials or cleaning up spills. Broken, damaged, or leaking vials should be handled with protective gloves as is done for sharps and infectious material. Take precautions to avoid accidental injection, contamination of wounds or skin abrasions, and contact with sharp materials or needles contaminated with IPs.

Full preparation instructions are detailed in a separate pharmacy manual.

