10.3. Analysis Sets

Safety Analysis Set: All patients who receive any study medication. Patients will be analyzed according to the treatment that they receive.

Modified intent to treat (mITT) Analysis Set: All randomized patients who receive any amount of study medication, have a baseline and at least one post-baseline efficacy assessment. Patients will be analyzed according to the treatment that they receive. This analysis set will be used for primary and secondary analyses.

Per Protocol (PP) Set: All randomized patients who receive the full designated amount of study medication according to the correct treatment assignment and who have results from HBV serology and viral markers at Day 85.

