3. STUDY(ANALYSIS) POPULATIONS

3.1 Modified Intent-to-treat population (mITT)

The modified Intent-to-Treat (mITT) population includes all randomized patients who receive any amount of study medication, have a baseline and at least one post-baseline efficacy assessment (i.e., at least one post-baseline measurement for one of the following parameters: qHBsAg, HBV DNA, HBcrAg and pg-RNA).

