5.3.2 Efficacy Analyses

Analyses of efficacy endpoints will be performed in the mITT population. In addition, sensitivity analyses will be performed in the PP population and will be considered supportive.

All parameters involved in any of the primary, secondary, or exploratory efficacy endpoints will be summarized according to their nature by treatment arm and overall. The original value for these parameters will be listed.

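### The primary efficacy comparison groups mITT patients by the treatment they mostly received, with no as-randomised analysis and no rule for an equal split of doses

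*SAP*

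**What the plan says.** Protocol 10.3 says of the mITT set: "Patients will be analyzed according to the treatment that they receive. This analysis set will be used for primary and secondary analyses". The protocol synopsis has the same rule.

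SAP 5.3 repeats it: "efficacy analyses will be performed using the mITT population, where patients will be in the treatment arm to which they received". The next sentence refers to a fuller description elsewhere and says that "patients will be analysed according to the treatment of the most treatment received". That description was not found in the protocol or the SAP.

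SAP 3.1 defines who belongs to the set ("The modified Intent-to-Treat (mITT) population includes all randomized patients who receive any amount of study medication", with baseline and post-baseline conditions) but does not say how members are grouped. SAP 3.2, on the Safety set, does say so: by treatment received. SAP 5.3.2 confirms that "Analyses of efficacy endpoints will be performed in the mITT population", with the per-protocol (PP) set as supportive. PP membership requires full dosing on the correct assignment.

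Disposition is handled differently. In SAP 5.2.1, for randomised patients, "the summaries will be provided by randomized treatment arms".

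**The concern.** Randomisation supports the Fisher or chi-square comparison when arm membership is fixed at randomisation. Here membership is settled afterwards, by what was dispensed and, for a patient given both products, by how many doses of each were received. Treatment received is a usual basis for a safety set. For primary efficacy it departs from the randomised comparison, and nothing in the plan restores that comparison: the PP set removes misdosed patients and does not return them to their own arm.

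Mixed dosing is possible. Protocol 6.3 gives six injections per patient, and under Protocol 6.5 pharmacy staff prepare each dose. Protocol 6.1.2 has unblinded site staff reconstitute the product in five countries, while "In the UK and Germany, reconstitution of IP will be done at a centralized location". The two documents also treat mixed dosing differently. The protocol has no majority rule, so its wording leaves a mixed-dose patient undefined. The SAP has one but does not cover ties. A programmer working from SAP section 3 alone could reasonably take mITT to be as randomised, contrary to 5.3.

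The stake is a threshold decision. SAP 5.3 calls the study exploratory but declares proof of concept at two-sided p<0.05, and the planned placebo response rate is only 3%.

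**Working it through.** 1. **The plan's own figure.** Inputs from Protocol 10.2: 3% vs 25%, two-sided 0.05, about 80% power, 40 per arm. The pooled formula is n = [z₀.₉₇₅√(2p̄(1−p̄)) + z₀.₈₀√(p₁(1−p₁)+p₂(1−p₂))]² / (p₁−p₂)². With p̄ = 0.14 this is [1.960×√0.2408 + 0.8416×√0.2166]² / 0.22² = 1.832/0.0484 = 37.85, so 38 per arm. Exact enumeration of Fisher's test at 40 per arm gives 78.0% power. The design figure reproduces and is not in dispute.

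2. **When a patient changes arm.** With k doses received, a majority of wrong doses needs w > k/2, so the smallest w is ⌊k/2⌋+1. For k = 6, 5, 4, 3, 2, 1 that is w = 4, 3, 3, 2, 2, 1. Ties, which have no rule, arise at k = 6 (3/3), 4 (2/2) and 2 (1/1).

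3. **Effect of one moved patient.** The counts are assumed for illustration. As randomised: 8/40 HepTcell vs 1/40 placebo. One HepTcell-randomised responder who mostly received placebo is regrouped: 7/39 vs 2/41.
   - Fisher, the Protocol 10.4.1 test: p = 0.0289, then 0.0838.
   - Which test the SAP would use: SAP 5.3.2.1 takes Fisher only if at least 80% of cells have expected counts below 5. With 9 responders in 80 patients, the expected responder counts are 9×40/80 = 4.5 per arm before the move, and 9×39/80 = 4.39 and 9×41/80 = 4.61 after it. The non-responder cells are far above 5. Two of four cells is 50%, so chi-square is selected.
   - Uncorrected chi-square, z = (p₁−p₂)/√[p̄(1−p̄)(1/n₁+1/n₂)] with p̄ = 9/80 = 0.1125. Before: 0.175/√(0.09984×0.05) = 2.477, p = 0.013. After: (0.1795−0.0488)/√(0.09984×0.05003) = 1.849, p = 0.064.

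   Under either test this table crosses 0.05 when one patient moves.

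4. **What as-randomised grouping would cost in power.** Assume m patients per arm receive wholly the other product. The arm rates become [0.25(40−m)+0.03m]/40 and [0.03(40−m)+0.25m]/40; for m = 1 these are 0.2445 and 0.0355. Fisher power for m = 0, 1, 2, 4 is 78.0%, 72.3%, 66.1% and 53.3%. With no misdosing nothing changes: N, alpha and power stay as planned.

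**The case against.** The harm is wholly conditional. If nobody is misdosed, the two groupings are identical, and the documents report no misdosing. Controls exist: under Protocol 6.5 the pharmacist consults the IWRS and doses are prepared against the randomisation list. Protocol 9.6 treats departures from the assigned dose as deviations, and SAP 5.2.2 reviews deviations before each lock. Site versus central preparation shows that error is possible, not that it is likely. All of this stands and limits the expected size.

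The rule is also prespecified and in substance shared by both documents, in a study the SAP calls exploratory. That stands too, but prespecifying a grouping does not make it a randomised one.

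A difference between arms would not be hidden. SAP 5.2.1 also summarises each population by treatment, and SAP Appendix 1 plans randomisation and drug-administration listings, so as-randomised results could be derived. This answers a worry about concealment but does not supply the analysis.

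Four stronger readings are tempting and are not supported:
- A reader might infer that any dispensing error moves a patient. It does not: someone who completes six doses with one or two wrong ones stays in the randomised arm.
- A reader might infer that one regrouped patient always changes the conclusion. Take 7/40 vs 1/40 and move one placebo-randomised responder to HepTcell, giving 8/41 vs 0/39. Fisher crosses 0.05 (0.057 to 0.005), but the chi-square test that SAP 5.3.2.1 would select is significant both times (0.025 and 0.004).
- A reader might infer that the Week 24 result was affected. The documents say only that the primary and secondary endpoints were not met.
- A reader might infer that the rule was introduced after unblinding. SAP version 2.0 postdates that analysis, but its history names the non-parametric model, minor issues and modified outputs, and the protocol already groups by treatment received.

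**Conclusion.** The point holds at modest size. The stated rule makes arm membership in the primary and secondary efficacy analyses depend on events after randomisation, ties have no rule, and no as-randomised efficacy analysis is planned. The effect is zero without misallocation. With it, a single patient can carry the primary test across 0.05 when responder counts are small, as in the worked table. That illustration rests on counts chosen near the threshold and on the moved patient being a HepTcell-randomised responder; it is not an estimate of what happened. The wording should be corrected and the facts on treatment received reported. Nothing in the documents shows that the trial's conclusion is wrong.

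**What to change.** State in Protocol 10.3 (and the matching synopsis text) and in SAP 3.1 and 5.3 that efficacy in the mITT set is analysed by the arm to which the patient was randomised. Remove the SAP 5.3 sentence on the treatment mostly received as far as it applies to efficacy; the tie problem then disappears for efficacy. Keep treatment received for the Safety set. Both documents need the edit because Protocol 10.6 lets the SAP supersede the protocol but holds the primary analysis fixed.

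The Week 24 analysis has already been run unblinded, so list this in SAP 5.3.17 as a change made after unblinding. The report should state whether any patient's received arm differed from the randomised arm. If none did, one sentence closes the matter. If any did, give the as-randomised primary and secondary results beside those already produced.

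The cost is a few sentences and, at most, a rerun on existing data, with no new patients and no change to sample size or alpha. If misdosing did occur, the as-randomised comparison will be somewhat diluted, as the power figures in the working show.

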4.3. Rationale for Study Design

The study design replicates the general design of the prior Phase 1 study but extends treatment from 3 to 6 doses and the follow-up after the last dose of study medication from 30 to 52 weeks. These modifications will enhance the effects of study medication and provide a more extended follow-up to assess the durability of immunogenicity and AEs. Diaries will be collected for reactogenicity events at visits on Days 8 and 36, which correspond to 7±2 days after the first and second dose of study medication. A visit consisting of a targeted physical examination will be conducted 7±2 days after administration of Doses 1 and 2 of study medication. Safety laboratory testing (Table 3), including liver panel, for Doses 1 and 2 will be obtained during the visits conducted 7±2 after these doses of study medication. Safety laboratory for Doses 3, 4 and 5 will be obtained in the pre-treatment interval from 7 days after dose administration through the time that the next dose of study medication is administered. Safety labs after Dose 6 will be assessed at the Day 169 visit. Investigators will review the eligibility of all patients prior to dosing to determine if the next treatment is to be administered. Eligibility for the next treatment will include: 1) confirmation that patients did not meet a Stopping Rule (Section 7.1.1); 2) confirmation that the pre-treatment liver parameters are within acceptable ranges for treatment (Section 4.1); 3) confirmation that patients do not have a new confirmed or suspected IMC (Appendix 2). If abnormalities of ALT, AST, total bilirubin, direct bilirubin, or INR are reported after dosing is commenced, the monitoring and dosing rules of Section 4.1 will be applied. These procedures are considered sufficient to evaluate reactogenicity events, particularly after Doses 1 and 2, and guard

against hepatitis flares and liver function abnormalities that would preclude the scheduled administration of the next dose of study medication.

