- 1 If an authorized COVID-19 vaccine has been administered in proximity to a scheduled IP administration, a ± 3 day window is allowed for IP dosing.
- ^m After Day 169 or ET, only MAEs, NCIs and IMCs will be recorded.
- ⁿ A single blood sample will be collected for biobanking at the beginning of the study (prior to dosing on Day 1) and end of the study. This sample will be used for future analyses not specified in the protocol. Analysis will be limited to HBV serologic and HBV-specific DNA and RNA and patients' DNA will not be analyzed.
- ° Safety laboratory testing, including liver panel, for Doses 1 and 2 will be obtained during the visits conducted 7±2 days after these doses of study medication. Safety laboratory testing following Doses 3, 4 and 5 will be obtained in the interval from 7 days after dose administration and before the next dose of study medication is administered. Safety labs after Dose 6 will be assessed at the Day 169 visit.
- ^p Diaries will also be reviewed at the Day 85, Day 113, Day 141 and Day 169 visits

Table 2 Schedule of Events – Follow-up Period

	Follow-Up Period					
Study Visit	Day 232	Day 323	Day 414	Day 505 or ET ^a		
Completion of Week (number)	33	46	59	72		
Window (days)	±10 days	±10 days	±10 days	±10 days		
Visit may be conducted at home or work or in part as a telemedicine visit ^b	X		X			
Immunosuppressive medications, vaccines, and new HBV treatments (only) ^c	X	X	X	X		
Targeted and symptom-driven PE	X	X	X	X		
Height and weight				X		
Vital signs ^d	X	X	X	X		
ECG ^d				X		
Hematology and serum chemistry	X	X	X	X		
Liver panel	X	X	X	X		
HBV serology and viral markers ^e		X		X		
Whole blood for PBMC isolation		X		X		
MAEs, NCIs and IMCs (only) ^f	X	X	X	X		

AE = adverse event; ECG = electrocardiogram; ET = early termination; HBV = hepatitis B virus; HIV = human immunodeficiency virus; MAE = medically-attended adverse event; NCI = new-onset chronic illness; IMC = immune-mediated medical condition; PBMC = peripheral blood nonnuclear cell; PE = physical examination.

^a If a patient prematurely discontinues study medication before Day 505, Day 505/Early termination procedures will be performed.

^b A telemedicine visit would include a home visit by appropriate trained personnel to perform a target and symptom-driven physical and obtain vital signs and safety laboratories. The remaining portions of the visit may be conducted virtually by the study investigator.

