3.2 Safety population

The Safety Analysis population includes all patients who receive any study medication. Patients will be analyzed according to the treatment that they receive.

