5.3.3.7 Reactogenicity Events

Each patient will record local events, systemic events, and oral temperature in a diary daily for 7 days after each dose. Incidence of reactogenicity events will be analyzed by treatment arm and dose number.

The number of patients with injection site reactogenicity events and each of the solicited events (Redness, Swelling or hardening, Pain at injection site (without pressure), tenderness) as well as with systemic reactogenicity events and each of the solicited events (fatigue, fever, chills, headache, muscle aches, joint aches, nausea, vomiting, diarrhoea) will be shown.

Also, number of events will be estimated for grouped injection site reactogenicity events (Redness, Swelling or hardening, Pain at injection site (without pressure), tenderness) and grouped systemic reactogenicity events (fatigue, fever, chills, headache, muscle aches, joint aches, nausea, vomiting, diarrhoea). Each event will be counted once by day of registration in the patient's diary card (i.e.: if the same event is registered for 3 different days in the diary card of a specific dose, 3 events will be counted for that dose).

Summaries will be performed for All events and also according to the grade Mild, Moderate and Severe. The size of reaction for Redness and Swelling (or hardening) will be assigned with the measurement in cm, being Mild from 2.5 to 5, Moderate larger than 5 to 10 and Severe larger than 10. Patients may have self reported events under 2.5 cm as an event, but following formal guidance these will not be reported as reactogenicity event in the statistical analysis.

A listing of all events recorded in the diary card will be included.

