5.3.9 Missing Data and Outliers

5.3.9.1 Missing data

A missing data point for a given study visit may be due to any one of the following reasons:

- The visit did not occur
- The visit occurred but data were not collected or were unusable
- The patient permanently discontinued from the study before reaching the window for the study visit

In general, missing baseline data will not be imputed. The following approaches are default methods for missing data handling in summary tables:

- Categorical data at baseline will be summarized for each treatment arm using counts (n) and percentages (%). Unless otherwise specified, denominators for all percentages will be the total number of patients in the corresponding treatment arm and dose number (if applicable) within the population of interest.
- Continuous data: The analyses and summaries for variables with continuous scales will be based on observed data only. Only available data will be used.
- In general, change from baseline is calculated only for patients with non-missing values for both the baseline and the time-point of interest and will be missing otherwise.

Missing data commonly encountered during the study may comprise:

- Missing/Partial Dates: For incomplete days or months, an imputation will be done by assigning the first day of month or the first month of year, respectively. For incomplete years in dates for measurements after randomization, the year of first dose date will be assigned.
- Continuous variables: mixed models are robust to the presence of missing at random and conducts the analysis with all participants despite the presence of missingness. Of note, this method calculates the estimations based on the variance-covariance structure but without any formal imputations.

Missing data commonly encountered for safety and background variables may comprise:

- Missing/Partial Dates for AEs:

Missing or partial AE onset dates and times will be imputed so that if the partial AE onset date/time information does not indicate that the AE started prior to treatment or after the TEAE

period, the AE will be classified as treatment-emergent. These data imputations are for categorization purpose only and will not be used in listings. No imputation is planned for date/time of AE resolution.

Missing/Partial Dates for Concomitant Medications:

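### Reactogenicity percentages default to all dosed patients, so a patient with no diary counts as reaction-free; use patients with diary data as the denominator

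*SAP*

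**What the plan says.** SAP 5.3 gives the default for every percentage: "The denominator for all percentages will be the total number of patients in the treatment arm and dose number (if applicable". The sentence goes on to limit this to patients "within the population of interest, unless stated otherwise in the table footnote". SAP 5.3.9.1 repeats the rule: "Unless otherwise specified, denominators for all percentages will be the total number of patients in the corresponding treatment arm and dose number (if applicable". The bullet holding that repeat opens with baseline categorical data, but its wording covers all percentages.

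Safety summaries use the Safety Population, and Appendix 1 lists Table 14.3.5.1 on that set. SAP 3.2 defines it: "The Safety Analysis population includes all patients who receive any study medication". The SAP defines no set of patients with diary data.

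On the source of the data, SAP 5.3.3.7 says: "Each patient will record local events, systemic events, and oral temperature in a diary daily for 7 days after each dose". On the analysis it says: "Incidence of reactogenicity events will be analyzed by treatment arm and dose number". It gives no denominator of its own, does not ask for a count of returned diaries, and has no rule for absent or partly completed ones. SAP 5.3.9.1 deals with missing dates, causality, severity and white-cell differentials, but not with diaries.

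Collection timing differs by dose. Protocol 4.3 says for Doses 1 and 2: "Diaries will be collected for reactogenicity events at visits on Days 8 and 36". For the later doses, a footnote to Table 1 in Protocol 4.6 says: "Diaries will also be reviewed at the Day 85, Day 113, Day 141 and Day 169 visits".

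**The concern.** The incidence and severity of local and systemic reactogenicity is a named safety endpoint (Protocol 3.4, SAP 4.3). If the table is built from diaries but divided by everyone dosed, an absent diary is treated as a diary reporting no reaction. That error can only lower the reported rate.

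Elsewhere the SAP handles missing safety data cautiously or openly. A missing causality assessment is tabulated as possibly related, and an adverse event whose severity is missing throughout gets its own category. The diary has no such rule, so the general default applies, and it works in the product's favour. SAP section 2 describes HepTcell as well tolerated, and reactogenicity rates are part of the evidence for a statement of that kind.

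**Working it through.** The plan states no reactogenicity rate and no diary return rate, so there is no planned figure to reproduce. The check follows the denominator rule and then shows its effect over an assumed range.

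**Inputs**
- Patients per arm: 40, the planned number in SAP 5.1, taken here as all receiving the dose in question.
- r, the share of dosed patients with a diary: assumed 80% to 100% (32 to 40 diaries).
- p, the incidence among patients with a diary: assumed 50% or 25%, for illustration.
- q, the incidence among dosed patients without a diary: unknown, and set equal to p unless stated.

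**Formulas**
- Reported incidence under the default = reactors with a diary / all dosed = p × r.
- True incidence among all dosed = p × r + q × (1 − r).
- Shortfall of the default = q × (1 − r). With q = p this is p × (1 − r), a relative understatement of 1 − r.
- Incidence with patients with diary data as denominator = p.

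**Results with q = p**

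| Diaries returned of 40 | r | Default, p = 50% | Default, p = 25% | Relative shortfall |
|---|---|---|---|---|
| 40 | 100% | 50.0% | 25.0% | 0% |
| 38 | 95% | 47.5% | 23.75% | 5% |
| 36 | 90% | 45.0% | 22.5% | 10% |
| 34 | 85% | 42.5% | 21.25% | 15% |
| 32 | 80% | 40.0% | 20.0% | 20% |

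Dividing by patients with diary data returns 50% or 25% in every row.

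**If return differed by arm (hypothetical)**
- Equal 50% incidence, 38/40 against 32/40 returned: 47.5% − 40.0% = 7.5 points of false difference, which is 3 patients in 40.
- Incidence 50% against 20%, with 32/40 and 38/40 returned: 0.50 × 0.80 − 0.20 × 0.95 = 0.40 − 0.19 = 21 points, where 30 is correct.

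**Dependence on q = p**
- If non-returners never react (q = 0), the shortfall is 0 and the default is right.
- The diary-based denominator errs upward by p − [p × r + q × (1 − r)] = (p − q) × (1 − r). The two errors are equal in size when q = p/2. With p = 50%, q = 25% and r = 80%, the true rate is 0.40 + 0.05 = 45%, the default gives 40% and the diary-based figure 50%.
- The diary-based denominator is therefore closer to the truth whenever non-returners react at more than half the rate of returners.

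**The case against.** The strongest reply is that the SAP does not fix this denominator as firmly as the default suggests. The sentence in 5.3 allows a table footnote to override it, and Appendix 1 is only an index of titles, so the footnotes cannot be seen. That stands as a limit on certainty. Still, no exception for reactogenicity is stated anywhere, and a plan followed as written uses the default.

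Second, section 5.3.3.7 speaks of numbers of patients and events, not percentages. That is correct. The percentages come from the general rule for categorical data in SAP 5.3 and from Protocol 10.4.3. A table giving only counts beside the arm size would invite the same division.

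Third, a patient without a diary is not wholly unobserved. Protocol Table 1 has a visit-level row that includes reactogenicity, and a severe systemic event is a Stopping Rule. A reader might infer that the diary is the only source of reaction data; the protocol does not support that. What remains is that SAP 5.3.3.7 describes diary-based incidence and gives no route for visit-level reports to enter the table.

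Fourth, a reader might infer that diary loss rises with dose number and creates a false decline in reactogenicity, because diaries for Doses 3 to 6 are reviewed about 28 days after dosing (for example, Day 57 to Day 85) and those for Doses 1 and 2 about 7 days after. The documents give no return data. The later reviews also fall at visits that Table 1 does not mark for home or telemedicine conduct, whereas Days 8 and 36 may be handled that way. The direction is therefore not established. The same holds for unequal return by arm.

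Finally, no reactogenicity test is planned, and Listing 16.2.9.1 would let a reader look for missing diaries. This limits the consequence but does not correct the table.

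**Conclusion.** The point holds as a gap in the rule with a known direction and an unknown size. Under the default denominator, a dosed patient without a diary is counted as reaction-free in the diary-based incidence. The relative understatement equals the fraction of missing diaries, provided non-returners react at the same rate as returners. Over an assumed return of 80% to 100% it is 0% to 20%, or 0 to 10 points at an incidence of 50%. It is zero if every diary is returned, and smaller if non-returners react less often.

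The documents do not show that any diary is missing, that return differs by arm, or that it falls with dose. The dose number in the rule is most naturally read as patients who received that dose, so missed doses are not the problem; absent or blank diaries among those dosed are. The correction is worth making because the endpoint is named, the default can only err downward, and the remedy is small.

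**What to change.** In SAP 5.3.3.7, or as a footnote to Table 14.3.5.1:

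- For each arm and dose, use as denominator the patients who received that dose and have diary data for it. Oral temperature is recorded daily, so a completed diary with no reactions can be told apart from an absent one.
- Show the number dosed and the number with diary data side by side, by arm and dose, so that any difference in return is visible.
- State how partly completed diaries are counted. Counting a patient with a single completed day as fully observed leaves the same downward error on a smaller scale. Showing also the number with all 7 days completed would make this visible.

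The cost is a sentence or footnote and a changed denominator in one table. The addendum describes its tables as supplementing those made for the Week 24 interim analysis, and Table 14.3.5.1 is not among them, so it may already exist and need to be re-run. Appendix 1 marks it for the final report. Reported rates would rise slightly, or stay the same if all diaries were returned.
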